2. GOALS

2.1. Main goal

To estimate prevalence and, in medium term basis (12 months), incidence of hyperkalaemia in heart failure (HF) outpatients with reduced ejection fraction (REF) and its relationship with non-optimal HF therapy and clinical outcomes (mortality and hospital admission).

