2.2. Specific goals

- a. - Estimating Hyperkalaemia prevalence in these patients.
- b. - Assessing the role of hyperkalaemia with the use of non-optimal therapy doses.
- c. - Estimating 12 months hyperkalaemia incidence on these patients and describing the severity of the episodes.
- d. - Estimating incidence of HF hospital admission and/or death in these patients on a medium term basis (12 months) and its association with existence of hyperkalaemia during follow up.
- e. - Assessing hyperkalaemia risk during follow-up in relation with the existence of diabetes and/or renal failure (RF) at baseline visit.

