5. Not having completed HF drug titration stage at the moment of inclusion (this stage is not completed if, on doctor's judgement, possible maximum doses have not been reached in RAA system drugs and any of these drugs has been included or dose-modified in recruitment visit)
6. Informed consent refusal

At any time during follow-up patients can leave the study (and will be censored in the analysis) or retire their consent (and will be excluded from the analysis).

3. 2. Considerations about simple size

Assuming a 10% risk of outcomes (mortality or HF hospital admission) among the exposed (hyperkalaemia), 2.5% among the non-exposed and a 7:1 non-exposed/exposed ratio, 73 exposed and 511 non-exposed patients should be included to have a 80% power to detect these differences with a 95% confidence level. The recruitment goal is set at 600 patients.

This sample size allows a precision of $\pm 2,4\%$, assuming a prevalence of hyperkalaemia at baseline of 10% and with a 95% confidence level. Furthermore, assuming 5% hyperkalaemia cumulative incidence through follow-up among hyperkalaemia-free patients at baseline, the proposed sample size, allows a precision of $\pm 1,8\%$ with a 95% confidence level.

3. 3. Selection of centres

The number of participant centres throughout Spain will be 20 and a cardiologist will be the principal investigator at every centre. The centres have been selected either among those with excellence-certified HF units, included in CiberCV Consortium or

with good performance in previous similar registries; this selection is not random, but based on interest and high performance criteria in the field of HF.

3. 4.- Source of information

Data will be obtained directly from the participants at the planned visits and completed with the review of their medical records if needed.

3. 5. Variables and CRF (appendix 1)

The main outcome variables are:

a.- Hyperkalaemia. Serum Potassium (K^+) will be measured in baseline and follow-up visits, but also if there is any intermediate hospital admission. All available potassium measurements during follow-up will be reviewed and values of hyperkalaemia identified. Hyperkalaemia will be considered with (K^+) Values $> 5,4$ mEq/L

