b.- Proportion of patients using drugs with proven efficacy for HF with REF -but also linked with hyperkalaemia- (ACEIs/ARB-II/ARNI and MRAs) and proportion of patients with use of optimal doses (based on current ESC heart failure guidelines²) of the same drugs; reason for not using them (or not receiving optimal doses) will be registered.

Proportion of patients in the following categories will also be computed:

- No ACEi/ARB/ARNI or at less than target dose and no MRA
- ACEi/ARB/ARNI at target dose and no MRA
- ACEi/ARB/ARNI at target dose and MRA at less than target dose
- ACEi/ARB/ARNI at target dose and MRA at target dose

c.- Hospital admissions during follow-up and main cause for them. Outcomes considered will include HF admissions caused by hyperkalaemia and related events. Outcome Serum (K^+) values will be also registered.

d.- Mortality and cause.

HF (and hyperkalaemia) hospital admissions and mortality will be independently considered as outcomes; joint outcome incidence of both will be also calculated.

The remaining variables are set out in appendix 1. The most important variables are defined in section 4.

3. 6. Study development

Every participating centre will include from inclusion date (as described in section 3.1) the first 30 heart failure outpatients who fulfil the inclusion criteria and none of the exclusion ones. The excluded patients will be also registered, pointing out the reason of exclusion. The data to be collected during the initial visit will include the variables described in Appendix 1: demographic, clinical, blood sample test, and functional. A follow-up and final visit will be scheduled after 12 months for collecting all the variables the study requires (Appendix 1). Hospitalisation data since inclusion visit will be also collected, together with the information of blood sample test performed in such period for detecting hyperkalaemia episodes. Mortality data will include date and cause, where possible. If follow-up visit cannot be conducted, the reason for it will be registered. The collection and management of data is described in section 5. The envisaged length of the study is 24 months since approval date.

3. 7. Limitations

Mild elevations of serum potassium that do not lead to hospital admission between planned visits may go unnoticed.

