6. PLAN FOR DATA ANALYSIS

Hyperkalaemia prevalence at basal visit and the rate of patients who do not receive and/or reach optimal doses of drugs of interest (ACIEs, ARB-II, MRAs) will be estimated and their corresponding 95% confidence intervals computed. The reason for not receiving and/or reaching optimal doses of drugs will be described, especially if it is due to hyperkalaemia.

For those patients who do not present hyperkalaemia at baseline, 12 month hyperkalaemia cumulative incidence (95% confidence interval) will be estimated; also it will be estimated the proportion of patients who have to modify their therapy due to hyperkalaemia.

The number of episodes of hyperkalaemia during follow-up in relation to the number of patients will be estimated and their severity and the therapy changes that induced described. Also 12 months cumulative incidence of clinical outcomes will be estimated: hospitalisation due to HF or to, hyperkalaemia (and related events) and mortality, considered as individual and composite outcomes. The association between hyperkalaemia and occurrence of outcomes will be analysed and also adjusted using potential confounding factors by means of logistic regression models

The quantitative variables will be generally described using either the mean and the standard deviation or the median and interquartile range according them following or not a normal distribution. When comparing groups, t-student test will be used for continuous variables and chi-square test for qualitative ones.

Both, intermediate and final analysis, are planned to be carried out after baseline-visit closure and at the end of follow up (12 months).

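### The admission outcome differs between the main goal, goal d with the sample size, and Section 6, and the version chosen decides which way hyperkalaemia-coded admissions can bias the association

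*Protocol*

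**What the plan says.** The protocol describes the admission outcome in several places, and the descriptions differ.

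- **Main goal (2.1, repeated in the Summary):** hyperkalaemia is to be related to "clinical outcomes (mortality and hospital admission". No cause of admission is given.
- **Specific goal d (2.2):** "Estimating incidence of HF hospital admission and/or death in these patients", together with its association with hyperkalaemia during follow-up.
- **Sample size (3.2):** sized on a "10% risk of outcomes (mortality or HF hospital admission" in the exposed, against 2.5% in the non-exposed.
- **Section 3.5c:** all admissions are collected with their main cause, followed by "Outcomes considered will include HF admissions caused by hyperkalaemia and related events". The closing lines of 3.5 then treat HF and hyperkalaemia admissions, and mortality, as outcomes both separately and jointly.
- **Section 6:** 12-month cumulative incidence of "hospitalisation due to HF or to, hyperkalaemia (and related events) and mortality", individually and as a composite. The association with hyperkalaemia is then modelled by logistic regression. Any-cause admission is not named.

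On how an admission is classified, 3.5a has potassium measured at any intermediate admission and 3.5c has it registered with the outcome. Section 4 defines neither an HF admission nor a hyperkalaemia admission. Section 5 makes the researchers responsible for the data and plans no data-quality monitoring, though an audit is possible. The text describes no adjudication.

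**The concern.** The association between hyperkalaemia and outcome is the quantity for which the study was sized. Goal d and 3.2 define that outcome one way, and the end of 3.5 and Section 6 define it another way. The difference is the hyperkalaemia admission, which is the type of event most closely tied to the exposure.

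If one main cause is assigned by someone who can see the potassium value, a patient admitted with decompensated HF and high potassium may be coded as hyperkalaemia. The same patient with normal potassium would be coded as HF. Under an HF-only outcome, this removes events from exposed patients only. If hyperkalaemia admissions are counted instead, an admission for hyperkalaemia alone makes the patient both exposed and a case, because goal d's exposure is hyperkalaemia during follow-up. The two definitions therefore fail in opposite directions, and an analyst choosing between them after seeing data could move the estimate either way.

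Separately, the main goal can be read as asking about admission for any cause. Those data are collected, but Section 6 lists no estimate for them.

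**Working it through.** **1. Which admissions each definition counts**

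| Admission | Any cause (main goal as worded) | HF only (goal d, 3.2) | HF or hyperkalaemia (end of 3.5, Section 6) |
|---|---|---|---|
| HF decompensation, main cause HF | yes | yes | yes |
| HF decompensation with high K+, main cause coded hyperkalaemia | yes | **no** | yes |
| Hyperkalaemia without HF decompensation | yes | no | **yes** (exposure is also outcome) |
| Other cause | yes | no | no |

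The 3.5c sentence, read literally, would count only those HF admissions that hyperkalaemia caused, which is a subset of the HF-only column. The second row is also lost from Section 6's individual HF-admission outcome.

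**2. Reproducing the plan's sample size**

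Inputs from 3.2: p1 = 0.10, p2 = 0.025, ratio 7:1, 80% power, 95% confidence (taken as two-sided, which reproduces the figure). Pooled-variance comparison without continuity correction:

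power = Φ{ [ (p1 − p2) − 1.96·√( p̄(1 − p̄)(1/n1 + 1/n2) ) ] / √( p1(1 − p1)/n1 + p2(1 − p2)/n2 ) }

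With n1 = 73 and n2 = 511:

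- p̄ = (7.3 + 12.775)/584 = 0.0344.
- The null standard error is 0.0228 and the alternative standard error is 0.0358.
- (0.075 − 1.96 × 0.0228)/0.0358 = 0.85, so power = 80.2%.

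The stated 73 + 511 is reproduced, so 3.2 contains no arithmetic error. The figure applies to death or HF admission only.

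**3. HF-only outcome: events lost to the hyperkalaemia code**

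Assumption (not in the protocol): a share m of exposed patients' composite events is lost, so the exposed risk is 0.10 × (1 − m). The non-exposed risk stays at 2.5%, where the odds are 0.025/0.975 = 0.02564.

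| m | Exposed risk | Odds ratio | Power (73 v 511) |
|---|---|---|---|
| 0 | 10% | 0.1111/0.02564 = 4.33 | 80% |
| 10% | 9% | 0.0989/0.02564 = 3.86 | 73% |
| 20% | 8% | 0.0870/0.02564 = 3.39 | 64% |

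Expected exposed events are 73 × 0.10 = 7.3, so these shares mean 0.7 to 1.5 patients.

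**4. HF-or-hyperkalaemia composite: exposure counted as outcome**

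Assumption: no true effect (2.5% in both groups), plus added hyperkalaemia admissions, which can occur only in the exposed.

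- Adding 2 points: risk ratio 4.5/2.5 = 1.8, with about a 21% chance of a significant excess in the exposed.
- Adding 5 points: risk ratio 7.5/2.5 = 3.0, with about a 59% chance.

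Without the added admissions that chance is 2.5%.

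**5. Any-cause admission**

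Assumption: other admissions add the same absolute risk to both groups. Adding 5 points (15% v 7.5%) gives 56% power, adding 10 points gives 43%, and adding 20 points gives about 30%.

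**The case against.** The strongest reply is that there are really two operative definitions. The main goal is a headline that goals a to e make specific, and goal d, the only specific goal on admissions, says HF admission. The 3.5c sentence says only what outcomes will include, and the closing lines of 3.5 agree with Section 6, so 3.5c looks like a language slip. Both readings are reasonable. They reduce the number of conflicts but leave the main one: goal d and 3.2 against the end of 3.5 and Section 6. An SAP could not settle that without choosing between statements in its own protocol.

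Three stronger readings are tempting, and the protocol does not support them.

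- **A reader might infer that the main goal's admission question goes unanswered.** All admissions are collected, Section 6 analyses the HF and hyperkalaemia ones, and an SAP not seen here may add an any-cause row. What can be said is that Section 6 does not name that outcome.
- **A reader might infer that HF admissions with high potassium drop out of the analysis and bias it towards the null.** Section 6's composite keeps them. The loss arises only under an HF-only outcome, and the composite has the opposite problem.
- **A reader might take the power loss as a forecast.** The 10% to 20% share is assumed. It is applied to a composite that includes deaths, which cannot be recoded in this way, so it implies a larger share of the HF admissions. It also assumes that the affected patients have no other HF admission and do not die within 12 months.

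Assignment of the cause at the site is itself inferred from 3.5c and Section 5. Appendix 1 (the CRF) is not shown and may record secondary causes or a coding rule. Because potassium is registered with the outcome, affected admissions could at least be identified and examined.

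**Conclusion.** The inconsistency holds and should be corrected. The main goal, goal d with 3.2, and the end of 3.5 with Section 6 describe different admission outcomes, and 3.5c needs rewording even if it is only a slip. The sample size is correct for death or HF admission and does not carry over to the other versions.

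Neither the direction nor the size of any bias is fixed by the documents. It can run towards the null under the HF-only outcome and away from it under the Section 6 composite. The illustrations depend on assumed shares and additions. With about seven exposed events expected, though, one reclassified admission is about 14% of them (1/7.3), so the result is sensitive to few coding decisions. This is an inexpensive improvement to the definition of the outcome. It does not show that the study cannot answer its question.

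**What to change.** 1. In 3.5c and the CRF, record HF decompensation yes/no for every admission. Count an HF admission whenever the answer is yes, whatever the main cause.
2. Make death or HF admission, so defined, the association outcome at the end of 3.5 and in Section 6, in agreement with goal d and 3.2. Report hyperkalaemia admissions separately and descriptively, outside the composite that is related to hyperkalaemia.
3. Either add any-cause admission, alone and with death, to Section 6 as a supplementary outcome for the main goal, stating that the study is not sized for it, or reword the main goal to HF hospital admission.
4. Correct the 3.5c sentence so that it agrees with point 2.

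Aligning 3.5c alone would not be enough, because the end of 3.5 and Section 6 would still count hyperkalaemia admissions.

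**Cost.** One CRF item, some rewording, and up to two extra outcome rows from data already collected. By the protocol's chronogram the eCRF is in design from January to March 2019 and first inclusion is in April 2019, so a version dated 18 February 2019 can still take the item. Any-cause admission is less specific to HF and would have lower power under the assumptions above, so it should sit beside the HF outcome and not replace it. The yes/no item remains a clinical judgement that may be made with the potassium value known. It reduces the dependence on the cause label but does not remove it.

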4. DEFINITION OF VARIABLES OF INTEREST

Heart Failure (HF) with reduced ejection fraction (REF): Patients with confirmed diagnosis of HF and with ejection fraction <40%.

Hyperkalaemia: K^+ values > 5,4 mEq/L.

Optimal doses: the maximum doses of renin-angiotensin-aldosterone related drugs that, according to the physician's judgement, the patient can receive. If any of these drugs (ACIEs, ARB-II, MRAs or sacubitril-valsartan) is *de novo* introduced at the initial visit, optimal doses will be not considered established.

A previous personal history of diseases and/or outcomes will be registered according to the usual practice of every centre. Some of the clarifications needed in every case are indicated as follows:

- **Coronary artery disease.** Documented existence of any of the following: acute myocardial infarction (AMI), acute coronary syndrome (ACS), coronary revascularisation (Percutaneous Coronary Angioplasty –PCA - or CABG) or coronary stenosis > 50% of arterial lumen in imaging test.
- **Cerebrovascular diseases.** History of ischaemic/haemorrhagic stroke or carotid stenosis > 50% of arterial lumen in imaging test.
- **Peripheral artery disease.** Aneurysm of thoracic/abdominal aorta or lower limb peripheral arterial disease.
- **Death due to a major cardiovascular event.** Due to ACS, HF, arrhythmia (sudden death), arterial aneurysm rupture or stroke.
- **Arterial thromboembolism.** Embolism phenomenon affecting arterial territory – (except pulmonary territory).
- **Ischaemic stroke.** Focal neurological deficit originated by cerebral ischemia; persists more than 24 hours after a sudden onset.

- **Haemorrhagic stroke:** Focal neurological deficit with sudden onset and originated by intracranial haemorrhage.
- **Acute coronary syndrome (ACS):** Acute coronary event that present typical ECG alterations and/or enzyme elevation.
- **NYHA functional class:**

Functional class I	No limitation. Ordinary physical activity does not cause dyspnoea, fatigue or palpitations.
Functional class II	Light limitation of physical activity. Everyday activities cause dyspnoea, fatigue or palpitations
Functional class III	Moderate limitation of physical activity. Activities considered less intense that everyday ones cause dyspnoea, fatigue or palpitations. Patient, however, does not present resting dyspnoea.
Functional class IV	Inability to perform activities without limitations. Symptoms may be present even at rest

- **Anaemia**
Haemoglobin values <12 g/dl in blood sample tests performed during the previous 3 months are considered as anaemia; this is the lower value of the normal range for adult men and postmenopausal women.
- **Diabetes (and type)**
Considered when personal history reflects diabetes diagnosis (and type).
- **Arterial hypertension**
Personal history reflecting HTA established diagnosis and/or therapy with antihypertensive drugs
A hypertensive patient will considered as controlled when PA<140/85 mmHg.
- **Dyslipidaemia**
Considered when personal history reflects dyslipidaemia diagnosis.
- **Body mass index (BMI):**
 - Overweight: BMI (Kg/m²) 25-29,9
 - Obesity: IMC (Kg/m²) ≥30

- **Renal function.**

It will be assessed according glomerular filtration rate as follows:

Stage 1 (GFR>90 ml/min/1,73 m²)

Stage 2 (GFR ≥ 60 y <90 ml/min/1,73 m²)

Stage 3 (GFR ≥ 30 y <60 ml/min/1,73 m²)

Stage 4 (GFR ≥ 15 y <30 ml/min/1,73 m²)

Stage 5 (GFR <15 ml/min/1,73 m²)

When considered as a dichotomous variable, stages 1 and 2 will be considered normal and stages 3, 4 and 5 considered as *altered renal function*.

5. DATA COLLECTION AND MANAGEMENT

5. 1. Data collection

Consecutively, every researcher will handle and explain the information sheet to the patients that might fulfil de inclusion criteria (and do not present any exclusion criteria) and will ask them to sign the informed consent. Researchers must warrant the accuracy and completion of the data collected for the study. Data registered at CRF (Appendix 1) should be consistent with source documents used for their collection.

5. 2. Data management

Data will be collected during initial and follow-up visits and they will be integrated into a unique data base of the web platform. Researchers are responsible of the information included in the database and will access by means of personal login and password. The online platform will include ranges and rules to minimize errors in data registering.

5. 3. Quality assurance

To improve uniformity of interpretation of criteria and/or procedures among centers, researchers may contact the promoter, *Sociedad Española de Cardiología* at the *Agencia de Investigación de la SEC* in order to solve any questions or problems that arise during the study:

Agencia de Investigación de la SEC. [contact]. [contact].
[contact]

Or directly with the project office:

ODDS, S.L.; [contact]; Telf.- [name]; Fax.- [name]

While there is no planned monitorization of data quality, the promoter can, if convenient, carry out an audit of the participant centres in order to ensure the compliance with best practices during the study.

6. PLAN FOR DATA ANALYSIS

Hyperkalaemia prevalence at basal visit and the rate of patients who do not receive and/or reach optimal doses of drugs of interest (ACIEs, ARB-II, MRAs) will be estimated and their corresponding 95% confidence intervals computed. The reason for not receiving and/or reaching optimal doses of drugs will be described, especially if it is due to hyperkalaemia.

For those patients who do not present hyperkalaemia at baseline, 12 month hyperkalaemia cumulative incidence (95% confidence interval) will be estimated; also it will be estimated the proportion of patients who have to modify their therapy due to hyperkalaemia.

The number of episodes of hyperkalaemia during follow-up in relation to the number of patients will be estimated and their severity and the therapy changes that induced described. Also 12 months cumulative incidence of clinical outcomes will be estimated: hospitalisation due to HF or to, hyperkalaemia (and related events) and mortality, considered as individual and composite outcomes. The association between hyperkalaemia and occurrence of outcomes will be analysed and also adjusted using potential confounding factors by means of logistic regression models

The quantitative variables will be generally described using either the mean and the standard deviation or the median and interquartile range according them following or not a normal distribution. When comparing groups, t-student test will be used for continuous variables and chi-square test for qualitative ones.

Both, intermediate and final analysis, are planned to be carried out after baseline-visit closure and at the end of follow up (12 months).

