1. BACKGROUND AND RATIONALE

In the last years, multiple reasons have been increasing the disease burden of heart failure (HF) in industrialised countries – also Spain –, being a very important health problem. It is foreseeable that this burden will continue increasing in our country¹.

In parallel with this evolution, several treatments already included in clinical practice guidelines^{2, 3}, have proved to be effective in selected groups of patients, especially those with systolic function impairment.

These treatments that interfere with the renin-angiotensin-aldosterone system, increase hyperkalaemia risk in HF patients as much as three times^{3, 4}. Hyperkalaemia is associated with conduction disorders and risk of potentially life-threatening arrhythmias; it is not rare at all, as 20 years ago estimations already indicated 1-10% prevalence in hospitalised patients⁵. More recent data among ACEI new users suggest in the first year 5,6% and 1,7% for potassium values >5 and >5,5 respectively.⁶ HF patients are at increased risk of hyperkalaemia, not only due to the drugs they receive (ACEIs/ARB-II, mineralocorticoids receptor antagonists (MRAs) and, more recently, sacubitril/valsartan), but also because of the frequent presence of comorbidities (diabetes or renal failure, among others).⁷

These drugs blocking the renin-angiotensin-aldosterone system have an IA indication in the clinical practice guidelines for patients with reduced ejection fraction, so their use is becoming more frequent and, subsequently, hyperkalaemia is a growing concern for treating HF patients.⁷

Despite the above mentioned, there is no evidence of prospective information for the estimation of hyperkalaemia problem in HF patients in the daily Spanish clinical practice, although some current registries allows an initial estimation of its prevalence. In a recent analysis of the patients included in Spain in the Heart Failure Registry of the European Society of Cardiology (ESC)⁸ 26,3% of patients (401/1526) where MRAs are indicated (REF), but not prescribed, the underlying reason for not prescription is Hyperkalaemia in 8,5% of them (34/401). There are many “not-prescriptions” that are not adequately justified, therefore hyperkalaemia has a larger prevalence (30,6%, 34/111) among cases where a cause for avoiding MRAs does exist. At least as important is the fact that the vast majority of patients, up to 3 of 4, do not reach the

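### The main goal asks how hyperkalaemia relates to non-optimal therapy, but section 6 plans only recorded reasons and attributed changes, with no comparison group

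*Protocol*

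**What the plan says.** Section 2.1 sets the main goal as the prevalence and 12-month incidence of hyperkalaemia and "its relationship with non-optimal HF therapy and clinical outcomes (mortality and hospital admission"). Specific goal b in section 2.2 is "Assessing the role of hyperkalaemia with the use of non-optimal therapy doses".

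For therapy, section 6 plans:

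- the rate of patients not receiving or not reaching optimal doses, with a 95% confidence interval;
- a description of reasons: "The reason for not receiving and/or reaching optimal doses of drugs will be described, especially if it is due to hyperkalaemia";
- in patients free of hyperkalaemia at baseline, "the proportion of patients who have to modify their therapy due to hyperkalaemia";
- a description of the therapy changes that hyperkalaemia episodes led to.

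The source of the reasons is section 3.5: "reason for not using them (or not receiving optimal doses) will be registered".

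For clinical outcomes, section 6 plans more: "The association between hyperkalaemia and occurrence of outcomes will be analysed and also adjusted using potential confounding factors by means of logistic regression models". The sentence just before it lists those outcomes as hospitalisation and mortality. A general sentence adds: "When comparing groups, t-student test will be used for continuous variables and chi-square test for qualitative ones". It names neither groups nor a therapy endpoint.

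**The concern.** A relationship between hyperkalaemia and non-optimal therapy is a contrast between patients with and without hyperkalaemia. Section 6 specifies that contrast for clinical outcomes but not for therapy. Each therapy item is either an overall rate or a count of cases that someone attributed to hyperkalaemia. Doses are also lowered or never reached for other reasons, and without a reference group that ordinary rate is never set against the rate in hyperkalaemic patients.

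The therapy part of the main goal would then report how often hyperkalaemia was recorded as the reason. It would not show whether patients with hyperkalaemia receive less RAA therapy than patients without it. This would be so even if section 6 were followed exactly. Section 6 also fixes no denominator for the share attributed to hyperkalaemia, and the Background shows that the choice matters.

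**Working it through.** **1. The plan's own figures (section 3.2).** Inputs: 10% against 2.5%, ratio r = 7, two-sided 5%, 80% power.

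- Exposed n = [1.96·√((1+1/r)·p̄(1−p̄)) + 0.842·√(p1(1−p1) + p2(1−p2)/r)]² / (p1−p2)², with p̄ = (0.10 + 7×0.025)/8 = 0.0344. Result: 73 exposed and 511 non-exposed, as stated (power 80.2%).
- Precision of prevalence: 1.96·√(0.10×0.90/600) = 2.4 points, as stated.
- Precision of incidence: 1.96·√(0.05×0.95/540) = 1.8 points, as stated.

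These figures are sound. They concern clinical outcomes, prevalence and incidence. Section 3.2 has no figure for therapy by potassium status.

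**2. Dependence on the denominator (section 1, cited registry, MRA non-prescription).** Inputs: 401 of 1526 indicated but not prescribed, 111 with a cause, 34 of these hyperkalaemia.

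- 401/1526 = 26.3%; 34/401 = 8.5%; 34/111 = 30.6%. All match the text, which says "hyperkalaemia has a larger prevalence (30,6%, 34/111) among cases where a cause for avoiding MRAs does exist".
- Ratio of the two shares: 30.6/8.5 = 3.6.
- Without a cause: (401 − 111)/401 = 290/401 = 72.3%.

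**3. What a baseline comparison could deliver.** Section 3.2 assumes 10% prevalence in 600, so about 60 with and 540 without hyperkalaemia. The protocol gives no rate of non-optimal therapy by potassium status, so the reference rate is an assumption, taken at three values. Half-width if both groups share that rate: 1.96·√(p(1−p)(1/60 + 1/540)).

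| Assumed reference rate | Half-width, points | Power for +15 points | Power for +20 points |
|---|---|---|---|
| 26.3% | 11.7 | 68% | 88% |
| 50% | 13.3 | 60% | 86% |
| 75% | 11.5 | 81% | >99% |

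**4. What a follow-up comparison could deliver.** 600 × 0.90 = 540 free of hyperkalaemia at baseline; 540 × 0.05 = 27 new cases and 513 without. With an illustrative 40% against 15% having a dose lowered or a drug stopped:

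- Half-width = 1.96·√(0.40×0.60/27 + 0.15×0.85/513) = 18.7 points around a difference of 25 points.
- Expected exposed events: 0.40 × 27 ≈ 11.

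The 27 is an upper limit under these assumptions. Restricting to RAA-drug users, and not counting hyperkalaemia first found at the 12-month visit, reduces it. With 20 exposed the half-width is 1.96·√(0.24/20 + 0.1275/513) = 21.7 points. With 15 it is 25.0 points, as large as the assumed difference. The size of the unexposed group hardly matters here.

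**The case against.** Four arguments on the other side deserve weight.

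- **A comparison may be intended.** Section 3.5 lists drug use and optimal dosing among the main outcome variables, so the word outcomes in section 6 could loosely include them. Section 6 also names a chi-square test, and an analysis plan that is not shown may add detail. This makes it wrong to say that the protocol rules a comparison out. It does not remove the point: the model follows directly on a list of clinical outcomes, the chi-square sentence names no therapy endpoint, and the method that section 6 does state for therapy is attribution.
- **Recorded reasons have value of their own.** A patient whose dose was cut for past hyperkalaemia may have normal potassium at baseline. The reason captures this and the measured potassium does not. This stands: the description should be kept, not demoted.
- **The registry figures prove less than they seem to.** A reader might infer from 290/401 that 72% of reasons will be missing here, or that physicians' reasons are unreliable. The documents support neither. The figures come from an earlier registry, concern only MRA non-prescription, and may mean that no valid cause existed rather than that none was written down. For below-target MRA doses the Background says only that hyperkalaemia was the reason in 10%. The 8.5% and 30.6% answer two different questions; the 3.6-fold gap is not measurement error.
- **Timing is hard to establish.** Scheduled potassium falls at baseline and 12 months, section 3.7 concedes that mild rises between visits may be missed, and no text shown provides dates for dose changes. This stands and limits the fix.

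**Conclusion.** The point holds in this form: for the therapy part of the main goal and for goal b, section 6 states a method that cannot show a relationship, because it rests on attribution and has no reference group. The registry example shows that an attributed share needs a stated denominator (8.5% or 30.6% from the same 34 patients); it shows no more than that.

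A reader might also infer that a measured comparison would settle the question. It would not. Under the section 3.2 assumptions the baseline contrast has a half-width of about 12 to 13 points, and the follow-up contrast about 19 points or more. These rest on the protocol's 600 patients, 10% prevalence and 5% incidence, and on assumed therapy rates that the protocol does not give. The sample-size figures in section 3.2 are not in question.

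One matter comes first. Section 3.5 bases optimal dose on the ESC guideline; section 4 bases it on the physician's judgement of what the patient can receive. Exclusion criterion 5 in section 3.1 removes patients whose titration is incomplete, so under the section 4 reading few included patients could be non-optimal. Until these passages are reconciled, the baseline endpoint is not defined.

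**What to change.** Reconcile the definitions of optimal dose in sections 3.5 and 4. Then amend section 6 as follows.

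- **Keep the reasons.** Show the share with no reason recorded, and state the denominator of every share attributed to hyperkalaemia.
- **Add a baseline comparison.** Give the proportion in each section 3.5 dose category by baseline hyperkalaemia, as risk differences with 95% confidence intervals. Label it cross-sectional, since past hyperkalaemia may already have lowered the dose. The four listed categories have no place for a patient with an ACEI, ARB or ARNI below target plus an MRA; the analysis needs one.
- **Add a follow-up comparison.** In patients free of hyperkalaemia at baseline and taking an RAA drug, compare the proportion whose dose category fell or whose drug was stopped by the 12-month visit, between those with hyperkalaemia detected before that visit and those without. Report the risk difference with its 95% confidence interval, adjusted for baseline dose category and GFR if the number of events allows. Potassium first found high at the 12-month visit should not count as preceding the change. Use ordering within follow-up only where dose-change dates are collected (Appendix 1 is not shown).
- **Report both as estimates**, not as powered tests.

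The cost is wording in section 6 and two analyses, with no extra visits, provided that doses are recorded at both visits. If dose-change dates are not in the case report form, adding them is extra data collection. The downside is a wide interval in the follow-up comparison.
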